### **3.2.22.1      Observed case**

Using this approach, a subject will be considered to have experienced a flare only if a subject has an ASDAS  $\geq 2.1$  at 2 consecutive visits or an ASDAS  $> 3.5$  at any visit during Part B up until Week 96. Only the subjects with at least one ASDAS score available at any post-baseline visit during Part B until Week 96 will be evaluable using this approach.

### **3.2.22.2      Alternative handling of premature withdrawal**

In this approach, a different handling of subject experiencing premature withdrawal from Part B at any point will be considered. Only subjects with a primary reason for premature withdrawal recorded as “adverse event” or “lack of efficacy” will be considered as having a flare. The other subjects experiencing premature withdrawal from Part B will not be considered as having a flare (unless other flare criteria are met).

### **3.2.22.3      Mixed model with repeated measures (MMRM) imputation of ASDAS**

In this approach, MMRM imputation of missing ASDAS values at any visit in Part B up until Week 92 because of subject premature withdrawal, of subject experiencing a flare or of missing assessment at a given visit will be performed. Consequently, using this approach, a subject will be considered as having experienced a flare only if a subject has an ASDAS  $\geq 2.1$  at 2 consecutive visits or an ASDAS  $> 3.5$  at any visit during Part B up until Week 92, taking into account both observed and imputed values.

The MMRM analysis is a special case of the mixed-effects regression model (Siddiqui et al, 2009) and can be generally written as:

$$Y = X\beta + Zv + \varepsilon$$

where  $Y$  is the continuous variable of which the missing value is estimated;  $X$  is the  $n \times p$  matrix of fixed effects in the model;  $Z$  is the  $n \times r$  matrix of variables related to the random component in the model;  $\beta$  is the  $p \times 1$  vector of regression coefficients for the fixed effects;  $v$  is the  $r \times 1$  vector of random subject effects; and  $\varepsilon$  is the  $n \times 1$  vector of the random residuals in the model.

The MMRM imputation of missing ASDAS values will be performed using an ANOVA/ANCOVA type of MMRM with randomized treatment arm (PBO, CZP 200mg Q2W, CZP 200mg Q4W), visit (categorical, ie Week 48, 50, 52...), geographic region (North America, Western Europe, Eastern Europe and Asia) and mNY classification (mNY positive, mNY negative) included in the model.

The multiple visits for each subject are the repeated measures as random effect within each subject.

The covariance structure of the within-subject errors will be assumed to be unstructured. If the covariance structure does not allow for a stable solution, a variance component structure or alternatively an autoregressive first order structure will be used.

The resulting estimates of the regression model will be used for replacing the missing values of a variable. If one of the regressor variables is missing, the adjusted least-squares mean at the given visit will be used for replacing the missing value.

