### **3.2.22 Flare**

A subject is considered to have experienced a flare if a subject has an ASDAS  $\geq 2.1$  at 2 consecutive visits or an ASDAS  $>3.5$  at any visit during Part B up until Week 96.

If a subject has an intermittent missing ASDAS score (ie, a missing value at 1 visit but non-missing values at the previous and subsequent visit), then the missing value will be ignored and the occurrence of a flare will be based on the 2 available values.

If the ASDAS score is missing at 2 or more consecutive visits, then the subject will be considered to have experienced a flare (even if ASDAS scores are available after the missed visits).

There is also the possibility to report one unscheduled ASDAS between two scheduled ASDAS assessments. The same rules as for the scheduled ASDAS apply for the unscheduled ASDAS.

The unscheduled ASDAS will be taken into account for flare calculation for two consecutive visits if there are more than 13 calendar days between two consecutive ASDAS calculated dates.

If the ASDAS score is missing at 2 scheduled visits and unscheduled ASDAS entry present in between and not larger than 3.5, then the subject will not be considered to have experienced a flare.

Occurrence of a flare will be based solely on the observed ASDAS values and will not take into account any imputation of ASDAS. Occurrence of a flare will be determined based on the actual

data entered into the eCRF for the individual ASDAS components, not based on data from the interactive voice or web response system (IXRS).

If a subject prematurely withdraws from Part B at any point for any reason, then the subject will be considered to have experienced a flare.

If a subject was incorrectly identified as flared at any point in Part B due to late data entry in IXRS and went to escape Part B, then the subject will be considered to have experienced a flare.

Sensitivity analyses will be conducted using different approaches for definition of flare. These approaches are described hereafter.

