### **3.2.22.4 Referenced based multiple imputation of ASDAS**

Missing data for the ASDAS scores at any visit in Part B up until Week 92 because of subject premature withdrawal, of subject experiencing a flare or of missing assessment at a given visit will be handled at each visit via reference based multiple imputation as described below:

This procedure will use an imputation model developed based on data from the PBO group only (Mallinckrodt, 2013). The reference-based multiple imputation assumes that the statistical behavior of the CZP and PBO-treated subjects after discontinuing study medication becomes that of the PBO-treated subjects. Data collected after discontinuation of the double-blind study treatment for both the CZP and PBO groups will be considered missing. Multiple imputations are used to replace missing outcomes for CZP- and PBO-treated subjects who discontinued using multiple draws from the posterior predictive distribution estimated from the PBO arm.

For subjects with a non-monotone (intermittent) missing pattern, Markov chain Monte Carlo (MCMC) will be used to impute their missing intermittent ASDAS scores by randomized treatment, geographic region and mNY classification. This will be done only once for each subject in order to provide a dataset with monotone missing (seed will be 221).

Data are processed sequentially by repeatedly calling SAS® PROC MI to impute missing outcome data at visits  $t=1, \dots, T$ , where  $t=1$  is Week 48 and  $t=T$  is Week 92

*Initialization.* Set  $t=1$  (Part B Baseline visit)

*Iteration.* Set  $t=t+1$ . Create a data set combining records from CZP- and PBO-treated subjects with columns for covariates (geographic region and mNY classification) and outcomes at visits 1 to  $t$ . Outcomes for all CZP-treated subjects are set to missing at visit  $t$  and set to observed or previously imputed values at visits 1 to  $t-1$ . Outcomes for PBO-treated subjects are set to observed at visit  $t$  or observed or previously imputed values at visits 1 to  $t-1$ .

*Imputation.* Run MCMC to impute missing values for visit  $t$  using previous outcomes for visits 1 to  $t-1$ , geographic region and mNY classification. Note that only PBO data will be used to estimate the imputation model since no outcome is available for drug-treated subjects at visit  $t$ .

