### 3.2.23 Time to flare

The time to flare will be defined as follows:

- For subjects who meet the criteria for flare, the flare date will be defined as:
  - For subjects who first meet the criterion “ASDAS  $\geq 2.1$  at 2 consecutive visits”, the date of the second ASDAS score will be considered the flare date.
  - For subjects who first meet the criterion “ASDAS  $> 3.5$  at any visit”, the date of the corresponding ASDAS score will be considered the flare date.
  - The date of the ASDAS score is defined as the date the corresponding BASDAI/PtGADA assessments were performed and the CRP sample(s) was (were) collected. If the assessments were not performed on the same day, a conservative approach will be used, and the latest day will be taken as calculated ASDAS day.
- Subjects who discontinue the study without Withdrawal Visit will be treated as having experienced a flare at the next planned ASDAS visit. The final available ASDAS score date + 32 (4 Weeks + visit window) will be used as flare date. If Week 48 or Week 50 are last ASDAS visits, Week 48/Week 50 ASDAS date + 18. (2 weeks + visit window) will be used as flare date.
- Subjects who discontinue the study will be treated as having experienced a flare at the date of their withdrawal visit, if the last ASDAS visit date is not equal with the withdrawal date. If the withdrawal date is equal to the last ASDAS visit date, the same approach as for subject without Withdrawal Visit will be used for deriving the flare date.
- Subjects with missing ASDAS scores at 2 or more consecutive visits will be treated as having experienced a flare at the date of the second visit where the ASDAS score is missing, irrespective of whether the subject meets the flare criteria at a later time point.
  - If the date of the second missing ASDAS visit is available, the date of the visit will be used.
  - If the date of the second missing ASDAS visit is not available, the last ASDAS date + 60 (8 weeks + visit window) will be used as flare date. If Week 48 is the last ASDAS visits, Week 48 ASDAS date + 32. (4 weeks + visit window) will be used as flare date. If Week 50 is the last ASDAS visits, Week 50 ASDAS date + 46. (6 weeks + visit window) will be used as flare date.
- For subjects who complete the study without meeting the criteria for flare, the censored date will be the last possible date of the event, i.e. Week 96.

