#### Observed case

Using this approach, a subject will be considered to have experienced a flare only if a subject has an ASDAS  $\geq 2.1$  at 2 consecutive visits or an ASDAS  $> 3.5$  at any visit during Part B up until Week 92.

Consequently, unlike for the main approach, subjects who discontinue the study will be censored at the date of their Withdrawal Visit and subjects with missing ASDAS scores at 2 or more consecutive visits will be censored at the date of the second visit where the ASDAS score is missing. In case a subject has missing ASDAS scores at 2 or more consecutive visits and meets the flare criteria at a later time point, the subject will be considered to have experienced a flare and the flare date will be defined as described earlier in this section.

Only the subjects with at least one ASDAS score available at any post-baseline visit during Part B will be evaluable using this approach.

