The LOCF imputation will be done whether the data is missing, the subject discontinued prior to the time point assessed, or the data is considered missing due to start of escape treatment.

Unless otherwise stated, the following guidelines apply for the LOCF analyses:

- For missing post-baseline Part A assessments, only carry forward earlier Part A post-Baseline values. Screening and Part A Baseline values do not get carried forward to the Part A post-Baseline visits.
- For missing post Week 48 Part B assessments,
  - if the subject did not experience a flare in Part B, only carry forward earlier Part B post-Week 48 values,
  - if the subject experienced a flare in Part B, the assessment at Escape week 0 will be treated as the last assessment in Part B prior to escape treatment. For any missing post 48 Part B assessments up to the week of flare (the later visit if flare was based on 2 visits), carry forward earlier Part B post-Week 48 values. Assessments whilst on escape treatment are not to be used, therefore the assessment at Escape week 0 will be carried forward for all subsequent visits until Week 96. E.g if the subject experienced a flare at week 72 then the Escape Week 0 assessment will be carried forward for the assessments after week 72 in Part B (76, 80, 84, 88, 92 and 96)

- Week 48 values do not get carried forward to the Part B post-Baseline visits.
- Assessments during escape treatment will not be carried forward.
- The following continuous endpoints in Part B will be compared between treatment groups using a mixed model for repeated measures (MMRM). The pattern of missingness for these variables is assumed to be MAR. Subjects who enter Part B will have already demonstrated sustained remission through 48 weeks on CZP 200mg Q2W. Many of these subjects will be randomized to receive placebo and will, therefore, be more likely to experience a flare. Post-flare data for subjects experiencing a flare (in any treatment group) will be treated as missing for the MMRM analysis. It is further assumed that most subjects who discontinue at this late stage in the study (i.e. during Part B) will do so as a result of reduced efficacy. Therefore, missing efficacy data due to either flare or study treatment discontinuation should be dependent on the observed efficacy scores, but independent of unobserved data. For the following continuous endpoints in Part B, imputation of missing data will be performed using the MMRM approach:
  - ASDAS
  - BASDAI

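### Two binary sensitivity analyses of flare (MMRM imputation and reference-based MI) and observed-case time to flare stop at Week 92, while the primary flare endpoint runs to Week 96

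*SAP*

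**What the plan says.** The primary definition in SAP Section 3.2.22 applies the ASDAS criteria "at any visit during Part B up until Week 96". Section 3.2.23 agrees for subjects who finish without a flare: "the censored date will be the last possible date of the event, i.e. Week 96". Table 3.3 also censors completers at Week 96.

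Section 8.1.3 repeats the primary analysis under four alternative flare approaches:

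- **Observed case (3.2.22.1):** Week 96. Subjects need at least one post-baseline ASDAS score "during Part B until Week 96 will be evaluable using this approach".
- **Alternative handling of withdrawal (3.2.22.2):** no window of its own. It changes only how withdrawals count and keeps the other flare criteria.
- **MMRM imputation (3.2.22.3):** "MMRM imputation of missing ASDAS values at any visit in Part B up until Week 92". The next sentence limits flare status to Week 92 as well.
- **Reference-based multiple imputation (3.2.22.4):** "Missing data for the ASDAS scores at any visit in Part B up until Week 92", with the final visit T in the imputation loop set to Week 92.

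For time to flare, the observed-case paragraph of Section 3.2.23 counts the criteria only "at any visit during Part B up until Week 92".

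**The concern.** Section 4.2 says the sensitivity analyses are there to test the robustness of the non-responder imputation used for the primary endpoint. For that purpose they should vary the handling of missing data and nothing else. MMRM imputation and reference-based MI are the only two binary approaches that impute missing ASDAS values, and both also drop the last assessment. If either result differs from the primary one, the reader cannot tell whether the cause is the missing-data assumption or the shorter window.

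Observed-case time to flare has a different problem: the SAP gives two answers for the same subject. Two programmers could implement it differently, and the choice should not be left open until after unblinding.

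**Working it through.** **1. Is Week 96 a usable ASDAS visit after Week 92?** Yes. Section 4.2 gives an example of a value "carried forward for the assessments after week 72 in Part B (76, 80, 84, 88, 92 and 96"). Section 8.2.2.2 fits the secondary MMRM for ASDAS to data up to Week 96.

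**2. Follow one subject.** The subject has no earlier flare, and has either ASDAS above 3.5 at Week 96 only, or ASDAS of at least 2.1 at Weeks 92 and 96.

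| Analysis | Section | Window | Result |
|---|---|---|---|
| Primary (NRI), also in FAS and PPS | 3.2.22, 8.1.3 | Week 96 | Flare |
| Binary observed case | 3.2.22.1 | Week 96 | Flare |
| Alternative withdrawal | 3.2.22.2 | none of its own | Flare |
| MMRM imputation | 3.2.22.3 | Week 92 | Non-flare |
| Reference-based MI | 3.2.22.4 | T = Week 92 | Non-flare, if status follows T |
| Observed-case time to flare | 3.2.23, text | Week 92 | Censored |
| Observed-case time to flare | Table 3.3 | no Week 92 limit | Event |

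Section 8.2.2.1 also asks for a Kaplan-Meier estimate by Week 96 and has it repeated under the observed-case approach. Under the text of 3.2.23, no event after Week 92 could enter that estimate.

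**3. Design figures.** Section 2.4 assumes 80%, 75% and 45% flare-free (Q2W, Q4W, placebo) with 70 per group, and states 98% and 94% power at two-sided 0.05. Exact power of Fisher's test with these inputs is 98.9% and 94.0%, so the stated power is sound. It concerns the primary endpoint and does not depend on the sensitivity windows.

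**4. Illustrative size.** The SAP gives no timing of flares. Assume a constant hazard over the 48 weeks of Part B. With p flare-free at Week 96, the proportion flare-free at Week 92 is p^(44/48).

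- Q2W: 0.80^(44/48) = 0.815; gain 1.5 points; 70 × 0.0150 = 1.1 subjects
- Q4W: 0.75^(44/48) = 0.768; gain 1.8 points; 70 × 0.0182 = 1.3 subjects
- Placebo: 0.45^(44/48) = 0.481; gain 3.1 points; 70 × 0.0310 = 2.2 subjects

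The unadjusted odds ratios against placebo are:

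- Q2W at Week 96: (0.80/0.20)/(0.45/0.55) = 4.89. At Week 92: (0.815/0.185)/(0.481/0.519) = 4.75.
- Q4W at Week 96: (0.75/0.25)/(0.45/0.55) = 3.67. At Week 92: (0.768/0.232)/(0.481/0.519) = 3.58.

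The Q2W difference from placebo falls from 35 points to 81.5 − 48.1 = 33.4 points.

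**5. Range.** Suppose instead that a share s of flares in every arm first arises after Week 92, so that the flare-free proportion at Week 92 is 1 − (1 − p)(1 − s).

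- s = 0: nothing changes.
- s = 15%: proportions 0.830, 0.7875 and 0.5325; 2.1, 2.6 and 5.8 subjects per 70 change status; the differences from placebo become 29.8 and 25.5 points. The Q2W odds ratio is (0.830/0.170)/(0.5325/0.4675) = 4.29.

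**The case against.** The strongest reply is that this is a small mismatch in supporting analyses. The primary test, the fixed sequence and the stated power do not change. In the illustration the shorter window reduces the apparent effect, so it does not flatter the drug. All of this stands.

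The illustration may also overstate the window effect. The 80/75/45% rates describe an endpoint in which withdrawal counts as failure: "If a subject prematurely withdraws from Part B at any point for any reason, then the subject will be considered to have experienced a flare". Two consecutive missed ASDAS visits count as well. Under MMRM imputation or MI neither is an automatic flare, so some of the events removed in the calculation would go whatever the window. This too stands, and the figures should be read as an order of magnitude.

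A reader might infer more than the documents support:

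- **That the sensitivity analyses in general stop at Week 92.** Two of the four binary approaches and the FAS and PPS repeats do not.
- **That a Week 96 flare becomes a success in observed-case time to flare.** It is censored, in a sensitivity analysis of a secondary endpoint with nominal p-values.
- **That the SAP states the MI outcome outright.** Section 3.2.22.4 limits which values are imputed but does not restate a flare window. The non-flare status is inferred from T.
- **That most of the lost flares are in the placebo arm.** With equal arms, placebo carries 3.1/(1.5 + 1.8 + 3.1) = 48% of the reduction.

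Week 92 might have been deliberate, because the MI model is fitted on placebo data only and that arm thins out. Nothing in the SAP says so, and Section 3.10 lists no shorter window. The Amendment 2 log records a global move of the censoring point to Week 96, which suggests that these paragraphs were missed. That origin is an inference, and the conflict in the current text does not depend on it.

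**Conclusion.** The inconsistency is real and sits in the current text. MMRM imputation and, on the natural reading of T, reference-based MI assess a shorter endpoint than the one they are meant to check. Observed-case time to flare conflicts with its binary counterpart, with Table 3.3 and with the Week 96 Kaplan-Meier estimate.

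The likely effect is about one to two subjects per arm of 70 and a small shift in the odds ratios. This rests on a constant hazard and the SAP's planning rates; the effect is smaller if flares come early in Part B and larger if they come late. It is a correction worth making before unblinding, so that the imputation-based checks can be interpreted. It is no threat to the primary conclusion.

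**What to change.** Replace Week 92 by Week 96 in:

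- Section 3.2.22.3, in both the imputation sentence and the flare-status sentence;
- Section 3.2.22.4, in both places, so that T is Week 96, with an added statement that flare status is derived through Week 96;
- the observed-case paragraph of Section 3.2.23.

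If Week 92 was intended, give the reason in Section 3.10 and bring Sections 3.2.22.1 and 8.2.2.1 and Table 3.3 into line with it.

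The cost is a few words and one more visit in the imputation models. That visit is the sparsest for the placebo-based MI: under the planning rates and constant hazard, about 0.45 × 70 = 31.5 placebo subjects are flare-free at Week 96, against 0.481 × 70 = 33.7 at Week 92. The loss is slight, and Section 3.2.22.4 already says what happens if there are too few placebo subjects to fit the model.

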### **3.2.22.4 Referenced based multiple imputation of ASDAS**

Missing data for the ASDAS scores at any visit in Part B up until Week 92 because of subject premature withdrawal, of subject experiencing a flare or of missing assessment at a given visit will be handled at each visit via reference based multiple imputation as described below:

This procedure will use an imputation model developed based on data from the PBO group only (Mallinckrodt, 2013). The reference-based multiple imputation assumes that the statistical behavior of the CZP and PBO-treated subjects after discontinuing study medication becomes that of the PBO-treated subjects. Data collected after discontinuation of the double-blind study treatment for both the CZP and PBO groups will be considered missing. Multiple imputations are used to replace missing outcomes for CZP- and PBO-treated subjects who discontinued using multiple draws from the posterior predictive distribution estimated from the PBO arm.

For subjects with a non-monotone (intermittent) missing pattern, Markov chain Monte Carlo (MCMC) will be used to impute their missing intermittent ASDAS scores by randomized treatment, geographic region and mNY classification. This will be done only once for each subject in order to provide a dataset with monotone missing (seed will be 221).

Data are processed sequentially by repeatedly calling SAS® PROC MI to impute missing outcome data at visits  $t=1, \dots, T$ , where  $t=1$  is Week 48 and  $t=T$  is Week 92

*Initialization.* Set  $t=1$  (Part B Baseline visit)

*Iteration.* Set  $t=t+1$ . Create a data set combining records from CZP- and PBO-treated subjects with columns for covariates (geographic region and mNY classification) and outcomes at visits 1 to  $t$ . Outcomes for all CZP-treated subjects are set to missing at visit  $t$  and set to observed or previously imputed values at visits 1 to  $t-1$ . Outcomes for PBO-treated subjects are set to observed at visit  $t$  or observed or previously imputed values at visits 1 to  $t-1$ .

*Imputation.* Run MCMC to impute missing values for visit  $t$  using previous outcomes for visits 1 to  $t-1$ , geographic region and mNY classification. Note that only PBO data will be used to estimate the imputation model since no outcome is available for drug-treated subjects at visit  $t$ .

Repeat steps 2a-2d, 20 times with different seed values to create 20 imputed complete data sets (seeds will be 51, 52, 53, 54, 55, 56, 57, 58, 59, 510, 511, 512, 513, 514, 515, 516, 517, 518, 519, 520, 221).

*Analysis.* For each completed data set, the flare status will be calculated using the complete datasets (with no missing data). Analysis as described in [Section 8.1.1](#) will be performed in order to provide treatment odds ratios, 95% CIs and the p-values from the proc MIanalyze.

If there are not enough PBO subjects available at the visits to impute the missing ASDAS values at the visits in Part B so that the model converted, no data will be presented in the corresponding table.

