### **2.4       Determination of sample size**

It is anticipated that approximately 210 subjects will be randomized in a 1:1:1 ratio to the CZP 200mg Q2W, CZP 200mg Q4W, and PBO treatment groups. The primary efficacy analysis is based on the proportion of subjects who do not experience a flare during Part B of the study. The proportion of subjects who do not experience a flare during Part B is assumed to be 80%, 75%, and 45% for the CZP 200mg Q2W, CZP 200mg Q4W, and PBO treatment groups, respectively. Given these assumptions, a sample size of 70 subjects per group provides 98% power to detect a significant difference between the CZP 200mg Q2W dose and PBO and 94% power to detect a significant difference between the CZP 200mg Q4W dose and PBO using a 2-sided significance level of 0.05.

Given that subjects enter Part B only if they have achieved sustained remission in Part A, it is necessary to estimate the number of subjects needed to enroll in Part A. It is assumed that approximately 28% of subjects enrolled in Part A will achieve sustained remission and qualify for Part B. This means that about 750 subjects will be enrolled in Part A in order to have 210 subjects who are randomized into Part B.

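### Read literally, the intermittent-gap step of the reference-based imputation uses 24 cells averaging 8.75 subjects for 13 visits, so not every cell can be estimated, and its single fill-in leaves uncertainty out

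*SAP*

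**What the plan says.** SAP section 3.2.22.4 describes a placebo-reference multiple imputation of ASDAS, used as a sensitivity analysis of the primary endpoint (section 8.1.3). It has two stages.

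- **Intermittent gaps.** For subjects with a non-monotone pattern, MCMC "will be used to impute their missing intermittent ASDAS scores by randomized treatment, geographic region and mNY classification". The SAP then fixes the number of runs of this stage, under seed 221, as follows: "This will be done only once for each subject in order to provide a dataset with monotone missing".
- **Sequential step.** Visits from Week 48 to Week 92 are then imputed one at a time from a model estimated on placebo data. Here region and mNY are called covariates, and the imputation is described as *using* them together with the earlier outcomes. This stage is repeated to give 20 completed data sets, and the results are combined.

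The only failure rule in the section applies when too few placebo subjects are available at the visits for the model to converge. In that case "no data will be presented in the corresponding table". No prior, pooling rule or minimum cell size is given for the intermittent stage. By contrast, the MMRM imputation in section 3.2.22.3 names simpler covariance structures to fall back on.

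**The concern.** The two stages treat the same factors in different words. The first imputes *by* arm, region and mNY; the second imputes *using* region and mNY. In a section that names SAS PROC MI, the natural reading of the first is a separate run for each combination of the three factors. A multivariate normal model over the whole ASDAS schedule would then be fitted in very small groups. This stage has to deliver monotone data before the placebo-based stage can start, so a failure here stops the analysis or forces an improvised repair after the data are seen.

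Separately, because the fill-in is done once, the filled values are carried into all 20 data sets as though they had been observed.

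**Working it through.** **Inputs**
- Sample size: "approximately 210 subjects will be randomized in a 1:1:1 ratio", so 70 per arm (section 2.4).
- Planned no-flare proportions: "is assumed to be 80%, 75%, and 45% for the CZP 200mg Q2W, CZP 200mg Q4W, and PBO treatment groups" (section 2.4).
- Factor levels: 3 arms, 4 regions, 2 mNY classes (section 3.2.22.3).
- ASDAS visits: spacing of 2 weeks after Weeks 48 and 50, then 4 weeks (the flare-date rules in section 3.2.23 and the carry-forward example in section 4.2). Imputation runs from Week 48 to Week 92.
- Post-flare efficacy data are treated as missing (section 4.2).

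**The plan's own figures first.** The SAP states that "a sample size of 70 subjects per group provides 98% power" for full dose against placebo, and "94% power to detect a significant difference between the CZP 200mg Q4W dose and PBO", at two-sided 0.05. The continuity-corrected normal formula is Φ[(d − 1/n − 1.96·√(2p̄(1−p̄)/n)) / √((p₁q₁+p₂q₂)/n)] with n = 70.
- 80% v 45%: (0.35 − 0.0143 − 0.1604)/0.0763 = 2.30, power 98.9%.
- 75% v 45%: (0.30 − 0.0143 − 0.1623)/0.0788 = 1.57, power 94.1%.

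Fisher's exact test gives 98.9% and 94.0%. The sample size and planning rates used below are therefore coherent.

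**Cells and visits**
- Cells: 3 × 4 × 2 = 24. Mean size: 210/24 = 8.75.
- Visits: 48, 50, 52, 56, 60, 64, 68, 72, 76, 80, 84, 88, 92 = 13.
- Parameters of an unstructured 13-visit normal model: 13 means + 13·14/2 = 91 variances and covariances = 104.
- A sample covariance from n subjects has rank at most n − 1. Nine subjects give rank 8; rank 13 needs at least 14 subjects.
- All cells at 14 would need 24 × 14 = 336 subjects, more than 210. This holds for any regional split.

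**Attrition at planning rates.** An average cell has 8.75 × 0.80 = 7.0 (full dose), 8.75 × 0.75 = 6.6 (half dose) and 8.75 × 0.45 = 3.9 (placebo) unflared subjects by Week 92.

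**Uneven splits (assumed; the SAP gives none), before attrition**

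| Region shares | mNY positive | Cells ≥14, of 8 per arm | Smallest cell |
|---|---|---|---|
| 25/25/25/25% | 50% | 0 | 8.75 |
| 10/30/50/10% | 60% | 2 | 2.8 |
| 5/20/65/10% | 70% | 1 | 1.1 |

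A dominant region rescues one or two cells per arm and makes the others smaller.

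**How many cells need the step (assumed rates; the SAP gives none).** With single-visit missing rate q at the 11 interior visits, a subject has a gap with probability s = 1 − (1 − q)¹¹, and an average cell contains one with probability 1 − (1 − s)^8.75. Gaps are taken as independent and attrition is ignored.

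| q | s | Cells of 24 with a gap |
|---|---|---|
| 0.5% | 0.054 | about 9 |
| 1% | 0.105 | about 15 |
| 2% | 0.199 | about 21 |
| 5% | 0.431 | about 24 |

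**Single fill-in.** With 20 imputations the combined variance is W + (1 + 1/20)·B, where W is the average within-imputation variance and B the between-imputation variance. Values filled once are identical in all 20 data sets, so they add nothing to B.

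**Alternative.** Running by arm only, with 3 region indicators and 1 mNY indicator, gives 13 + 4 = 17 variables for 70 randomized subjects per arm. By Week 92 about 70 × 0.80 = 56, 70 × 0.75 = 52.5 and 70 × 0.45 = 31.5 would be unflared.

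**The case against.** The SAP shows no program code, and one preposition is not a specification. If *by* only meant that the three factors enter the model, the step could be estimated. This stands as a limit on certainty: separate runs are the better reading, not a proven one. It does not remove the need to change the sentence, since two programmers could build different models from it.

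Four stronger readings are tempting, and the SAP does not support them.

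- A reader might infer that the step fails in most cells. Only cells with an intermittent gap need it, and at an assumed 0.5% per visit that is about 9 of 24. A few large cells may also be estimable, and an informative prior would let the algorithm run, though none is stated.
- A reader might infer that a sparse cell triggers the empty-table rule. That rule is confined to too few placebo subjects at the visits, which is the sequential stage. Sparse cells in the intermittent stage, including those in the active arms, have no stated handling.
- A reader might infer that this is the only sensitivity analysis departing from missing at random. The rule in section 3.2.22.2 classifies withdrawals by their recorded reason and is not a missing-at-random analysis either. What would be weakened is the only placebo-reference analysis.
- A reader might infer a material effect on the flare result. The SAP offers no basis for sizing it. A filled gap bears on flare status only if the value exceeds 3.5, or if it combines with or separates neighbouring values of 2.1 or more.

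**Conclusion.** The point holds in limited form. On the by-group reading, the intermittent stage cannot be estimated in every cell for any distribution of 210 subjects, because 336 would be needed. Any sparse cell with a gap would fail or depend on an unstated prior, and the SAP does not say what happens then. The number of such cells is not known. The single fill-in is a separate, smaller defect that holds under either reading: the combined variance is understated by an amount that depends on how many values are filled.

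The conclusion rests on the by-group reading, an unstructured normal model, and 13 visits inferred from the flare-date rules. Counting every two-weekly Part B visit listed in section 3.3 would give (92 − 48)/2 + 1 = 23 time points and make matters worse. The primary analysis with non-responder imputation is not affected.

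**What to change.** Amend the sentence in section 3.2.22.4 so that the intermittent MCMC step is run by randomized treatment only, with region and mNY as indicator covariates alongside the 13 visits. Generate it 20 times, one for each final data set, with a stated seed for each run.

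The cost is one sentence in the SAP and one change to the imputation call. The price in assumptions is a common covariance across region and mNY within each arm. The gain should not be overstated. The model starts from 70 subjects per arm against 17 variables, but at planning rates late placebo visits would rest on about 31 unflared subjects. That is above full rank but still thin.
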